8. STUDY ASSESSMENTS AND PROCEDURES

All study procedures and assessments together with their timing are summarized in the SoA in Section 1.3.

Protocol waivers or exemptions are not allowed. Adherence to the protocol requirements is essential.

8.1. Safety Assessments

The safety assessments listed in Section 1.3 should be followed during the 180-day extension study.

8.1.1. Complete Physical Examinations

A complete physical examination (PE) will be performed on Days 240 and 365/ET. The complete PE will include the following: an examination of the skin/integumentary systems, general appearance, head, neck (including thyroid), eyes, ears, nose, throat, lymph nodes, chest (lungs), heart, abdomen, musculoskeletal system, neurological system, and any additional assessments needed to establish Baseline status or evaluate symptoms or TEAEs. Any abnormalities should be categorized as clinically significant (CS) or not clinically significant (NCS), and clinically significant abnormalities should be recorded as TEAEs, TESAEs, or AESIs. Investigator or qualified medical personnel who routinely perform these evaluations in patients with ALS will conduct the examination, determine findings, and assess any abnormalities as to their clinical significance.

8.1.2. 12-Lead Electrocardiograms

12-Lead ECGs will be performed on Days 240 and 365/ET. Any clinically significant abnormalities are to be recorded as TEAEs. The ECG recording will be printed out and stored with the Participant's records.

8.1.3. Vital Signs

Vital signs will be measured on Days 240, 300, and 365/ET. After resting in the seated position for 5 minutes, vital signs will be recorded including temperature, sitting blood pressure, heart rate, respiratory rate, and oxygen saturation on room air. The method of temperature measurement should be according to the Site's policy and should be consistently applied.

8.1.4. Clinical Laboratory Assessments

The Investigator must review the Participant's laboratory test results reports, document this review, and record any clinically relevant changes occurring during the study. The laboratory reports must be filed with the source documents. Clinically significant abnormal laboratory findings are those that are not associated with the underlying disease, unless judged by the Investigator to be more severe than expected for the Participant's condition. Clinically significant abnormal laboratory findings should be recorded as TEAEs, TESAEs, or AESIs using an appropriate medical diagnosis.

Blood sample for laboratory assessments will be collected on Days 240 and 365/ET.

All protocol-required laboratory assessments must be performed in accordance with the laboratory manual and the SoA. The laboratory reports must be filed with the source documents.

8.1.4.1.1. Hematology

- White blood cell count
- Neutrophil count (including calculated absolute neutrophil count)
- Hemoglobin
- Hematocrit
- Platelet count

8.1.4.1.2. Kidney Function Tests

- Blood urea nitrogen (BUN)
- Creatinine

8.1.4.1.3. Liver Function Tests

- Aspartate aminotransferase (AST)
- Alanine aminotransferase (ALT)
- Alkaline phosphatase
- Gamma-glutamyl transpeptidase (GGT)
- Total bilirubin
- Total protein
- Albumin

8.1.4.1.4. Clinical Chemistry

- Electrolytes (sodium, potassium, chloride, bicarbonate, calcium, inorganic phosphate, magnesium)
- Glucose (random collection, i.e., not necessarily fasting)
- Amylase
- Lipase
- Lactate dehydrogenase
- Creatine kinase

8.1.5. Slow Vital Capacity

Slow vital capacity is a pulmonary function test that quantifies the volume of air that can be slowly exhaled after slow maximum inhalation. SVC will be measured and recorded on

Days 240, 300, and 365/ET. Clinically significant abnormal SVC findings should be recorded as TEAEs, TESAEs, or AESIs.

8.2. Other Assessments and Procedures

8.2.1. Revised Amyotrophic Lateral Sclerosis Functional Rating

The ALSFRS-R is a validated rating scale for measuring the global function of patients with ALS. It provides a health professional-generated estimate of the patient's degree of functional impairment, which can be evaluated serially to objectively assess any response to treatment or progression of disease. The ALSFRS-R includes twelve questions that ask the Investigator to rate his/her impression of the patient's level of functional impairment in performing one of twelve common tasks, e.g., climbing stairs. Each task is rated on a five-point scale from 0 (can't do) to 4 (normal ability). Individual item scores are summed to produce a reported score between 0=worst and 48=best. The ALSFRS-R will be conducted on Days 240, 300, and 365/ET. Details about the scale can be found in Section 10.4, Appendix 4.

8.2.2. Handheld Dynamometry

Muscle strength will be measured quantitatively by HHD and the change from baseline (Day 0, VMALS-002-2) in HHD following Engensis injections as compared to Placebo. HHD is a procedure by which a dynamometer is applied to the body of an individual being tested.⁶⁴

A non-AC powered dynamometer (manufactured by Hoggan Health Industries, Inc) will be used at all clinical sites. These measurements will be performed on Days 240, 300, and 365/ET. Strength measurements will be evaluated for individual muscles.⁶⁵

8.2.3. Quality of Life Assessment, Patient Reported Outcomes, and Clinical Reported Outcomes

8.2.3.1. Amyotrophic Lateral Sclerosis Assessment Questionnaire

The ALSAQ-40 is a disease-specific, Participant self-report health status, or electronic patient-reported outcome (ePRO). There are 40 questions in the ALSAQ-40 with 5 discrete scales: physical mobility (10 questions), activities of daily living and independence (10 questions), eating and drinking (3 questions), communication (7 questions), and emotional reactions (10 questions). The ALSAQ-40 will be measured on Days 240 and 365/ET. See Section 10.5, Appendix 5, for the ALSAQ-40 questionnaire.

Participants are asked to think about the difficulties that they may have experienced during the last two weeks (e.g., "I have found it difficult to feed myself"). Participants are asked to indicate the frequency of each event by selecting one of 5 options (Likert scale): never, rarely, sometimes, often, always, or cannot do at all.

8.2.3.2. Patient Global Impression of Change

The Participant's impression of change at Days 240 and 365/ET will be measured with the PGIC questionnaire through use of the ePRO. This questionnaire measures the Participant's perception

of their level of activity, symptoms, emotions, and overall quality of life during the study. Each descriptor is ranked on a 10-point scale, where Much Worse = 0, No Change = 5, and Much Better = 10. The PGIC questionnaire is presented in Section [10.6](#), Appendix 6.

Upon completion of the questionnaire by the Participant, the study coordinator will check the questionnaire for completeness. Any omissions or ambiguous answers will be clarified by the Participant prior to leaving the clinic.

8.2.3.3. Clinical Global Impression of Change

The CGIC is a validated instrument completed by observers as an assessment of QoL. The CGIC is a 8-point scale with scores that range from 0 (not conducted) to 1 (very much improved) to 7 (very much worse). The test will be administered during the Days 240 and 365/ET Visits. The CGIC questionnaire is presented in Section [10.6](#), Appendix 6.

8.3. Treatment-emergent Adverse Events and Treatment-emergent Serious Adverse Events

The definitions of TEAEs and TESAEs can be found in Section [10.2](#), Appendix 2.

8.3.1. Time Period and Frequency for Collecting TEAE and TESAE Information

All TEAEs and TESAEs will be collected after signing informed consent prior to, on, or after Day 180 of the Study VMALS-002-2 until the time that the Participant completes or withdraws consent for VMALS-002-2b (see definition of TEAE, Section [10.2](#)).

All TESAEs will be recorded and reported to the Sponsor or designee immediately and under no circumstance should this exceed 24 hours, as indicated in Section [10.2.5](#), Appendix 2. The Investigator will submit any updated TESAE data to the Sponsor within 24 hours of its availability.

Investigators are not obligated to actively seek TEAEs or TESAEs after conclusion of the study participation. However, if the Investigator learns of any TESAE, including a death, at any time after a Participant has been discontinued from the study, and he/she considers the event to be possibly, probably, or definitely related to the study intervention or study participation, the Investigator must promptly notify the Sponsor.

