
 To determine whether IM administration of Engensis has positive effects on survival in ALS Participants 	
 Time to all-cause mortality compared to Placebo

 To evaluate Quality of Life improvement following Engensis injections in ALS Participants compared to Placebo 	
 Change from Baseline (Day 0) in Quality of Life (QoL) using the ALS Assessment Questionnaire (ALSAQ; with 40 items, ALSAQ 40) on Day 365 for Engensis compared to Placebo

 To evaluate Patient and Clinical Reported Outcome improvement following Engensis injections in ALS Participants compared to Placebo 	
 Patient Global Impression of Change (PGIC) and Clinical Global Impression of Change (CGIC) at Day 365 for Engensis compared to Placebo

Overall Design

VMALS-002-02b is a Phase 2a, 6-month extension study, multicenter study designed to assess the long-term safety of Engensis (containing the active pharmaceutical ingredient VM202) in Participants with ALS.

Participants will be enrolled in the VMALS-002-2b study following the completion of the Day 180 Visit of Study VMALS-002-2. Participants will continue to be identified by the same Participant number.

Assessments to be conducted during this VMALS-002-2b extension study are as follows: vital signs; weight and height; complete physical examination; a record of all concomitant medications and procedures; ALSFRS-R; Handheld Dynamometry (HHD); Slow Vital Capacity (SVC); Amyotrophic Lateral Sclerosis Assessment Questionnaire, 40 questions (ALSAQ-40); Patient Global Impression of Change (PGIC); Clinical Global Impression of Change (CGIC); and urine pregnancy test for females of childbearing potential. Assessments of TEAEs, TESAEs, AESIs, and clinically significant laboratory values will continue from the Day 180 Visit of Study VMALS-002-2 throughout the VMALS-002-2b extension study, to Day 365.

Study and Treatment Duration:

There will be no treatments during this extension study. The timing for visits in the VMALS-002-2b study starts at the conclusion of the Day 180 Visit in VMALS-002-2. Participants in VMALS-002-2b will be followed for 180 days to Day 365.

Visit Frequency:

Consented Participants will be seen and evaluated for safety at visits every 60 days (Days 240, 300, and 365/ET).

Intervention Groups and Duration:

[figure not shown]

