1.2. Study Schema

1.3. Schedule of Activities (SoA)

	Day 240	Day 300	Day 365/ET
Visit Window (days):	± 7	± 7	± 7
Procedure			
1 Informed Consent (obtained prior, during or after the Participant's Day 180 Visit in Study VMALS-002-2)			
2 Vital Signs, Weight, Height	X	X	X
3 Complete Physical Examination	X		X
4 12-Lead ECG	X		X
5 Serum Chemistry, Hematology	X		X
6 Concomitant Medications and Procedures	X	X	X
7 Urine Pregnancy Test			X
8 SVC	X	X	X
9 ALSFRS-R	X	X	X
10 HHD	X	X	X
11 ALSAQ-40	X		X
12 PGIC and CGIC	X		X
13 TEAEs, TESAEs	↔	↔	↔
14 AESIs	↔	↔	↔

FOOTNOTES FOR THE SCHEDULE OF ACTIVITIES

Note: The Schedule of Activities includes activities during all Study Visits.

Order of Assessments during Visits (if assessment is to be performed): AEs/TEAEs, SAEs/TESAEs, vital signs and weight, ALSFRS-R, HHD, ALSAQ-40, pregnancy test, complete physical exam, SVC, 12-Lead ECG, concomitant medications and procedures, PGIC and CGIC, and blood sample collection for laboratory assessments (serum chemistry and hematology)

Abbreviations: AESI = adverse events of special interest; ALSAQ-40 = Amyotrophic Lateral Sclerosis Assessment Questionnaire, 40 questions; ALSFRS-R = Revised Amyotrophic Lateral Sclerosis Functional Rating Scale; CGIC = Clinical Global Impression of Change; Day 365/ET = Day 365 Visit or Early Termination; ECG = electrocardiogram; ET = early termination or withdrawal; HHD = Handheld Dynamometry; PGIC = Patient Global Impression of Change; SVC = Slow Vital Capacity; TEAE = treatment-emergent adverse event; TESAE = treatment-emergent serious adverse event

- Informed Consent** process is to be obtained prior to, during or after the Participant's Day 180 Visit in Study VMALS-002-2
- Vital Signs, Weight, and Height:** Vital signs and weight will be measured at Study Visits on Days 240, 300, and 365/ET (Day 365 or Early Termination). After the Participant has rested in the seated position for 5 minutes, vital signs will be collected, including temperature, sitting blood pressure, heart rate, respiratory rate, and oxygen saturation on room air. The method of temperature measurement should be according to the Site's policy and should be consistently applied.

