9.2. Population for Analysis: Safety Population

The safety analysis population will contain all Participants who enroll in VMALS-002-2b.

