10.3.2. Definitions

Active Infection	Chronic infection or severe active infection that may compromise the Participant's wellbeing or participation in the study, in the Investigator's judgment
Day 240, etc.	Day 240 (for example) refers specifically to the actual day of the Visit designated as the Day 240 Visit, and not to the 240 th day of the study for a Participant.
End of Study	Completion of the last Visit (Day 365) or procedures shown in the SoA for the last Participant remaining in the study
Highly Effective Contraception Method	See Contraceptive Guidance
Investigator	The PI or appropriate study site personnel whom the PI designates to perform a certain duty
Safety Analysis Population	All Participants in the study
Sponsor	Helixmith Co., Ltd. and its representatives contracted to provide services for study conduct
Participant	Anyone who is consented for the Safety Evaluation during VMALS-002-2b on or prior to Day 180 of VMALS-002-2
VM202	The active pharmaceutical ingredient of Engensis: a novel genomic complementary deoxyribonucleic acid (cDNA) hybrid human hepatocyte growth factor (HGF) coding sequence (HGF-X7) expressing two isoforms of HGF, HGF ₇₂₈ and HGF ₇₂₃

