6.1 Analysis Sets

6.1.1 Safety Analysis Population

The safety analysis population will contain all Participants who sign the Informed Consent of the VMALS-002-2b study. Participants will be grouped according to their actual treatment received in VMALS-002-2 study.

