6.2.4 Conventions for Missing and Partial Dates

All rules explained below for partial / missing dates will be followed unless contradicted by any other data recorded on the electronic Case Report Form (eCRF).

All dates presented in the individual subject listings will be as recorded on the eCRF (i.e., not completed as per the below rules).

6.2.5 Missing / Partial Start / Stop Date of Adverse Events (AE) and Concomitant Medications

Missing and partial start and stop dates will be imputed for analysis purposes as follows.

Partial or missing stop date will be imputed as follows:

If the stop date is completely missing and the event has resolved, or the subject has stopped taking the concomitant medication, the stop date will be imputed as the date of the subject’s last clinic visit in the study.

- If only the year is known, the stop date will be imputed as “31-Dec” of that year or as the date of the subject’s last clinic visit in the study if in the same year.
- If the month and year are known, the stop date will be imputed as the last day of that month unless the stop date corresponds to the same month as the subject’s last clinic visit in which case the date of subject’s last clinic visit in the study will be used instead.

Missing start date will be imputed as follows:

- If the stop date occurs on or after the start of study drug or the event / concomitant medication is ongoing, the start date will be imputed as the date of the first dose of study drug.

QMD Ref: Worldwide-TMP-ST-005-7.0 Effective: 12Aug2019	Governing QMD: Worldwide-SOP-ST-001
Confidentiality Statement	

This document is the property of Worldwide Clinical Trials Inc. and may not be duplicated, copied, altered or removed from company without prior approval from Worldwide Quality Assurance or in compliance with Worldwide Standard Operating Procedures.

Worldwide Clinical Trials Controlled Quality Management Document			
 WORLDWIDE CLINICAL TRIALS	Sponsor:	Helixmith Co., Ltd.	
Protocol Number:			VMALS-002-2b
STATISTICAL ANALYSIS PLAN. PHASE 2-3-4			

- If the stop date occurs before the start of study drug, the start date of the event / concomitant medication will be imputed as the subject's screening date or the stop date of the event / concomitant medication whichever is earlier.

Partial start date (year present, but month and day missing)

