In this study the adverse events (AEs) will be presented from collected since Screening visit of VMALS-002-2 study. AEs that registered as not treatment emergent (not TEAEs) will be presented in a separate listing and will not be tabulated. TEAEs will be tabulated in similar manner as two sets: TEAEs started at date of signing of IC for this study or later and all TEAEs collected during both studies. All AEs from both studies will be united for presenting in listings.

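### The start of the extension adverse-event window is stated inconsistently, and the SAP's consent-date start makes time at risk depend on when a participant signed

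*Protocol*

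**What the plan says.** **Consent timing.** Footnote 1 of the Schedule of Activities (Protocol Section 1.3) says the consent "process is to be obtained prior to, during or after the Participant's Day 180 Visit in Study VMALS-002-2". The synopsis (Number of Participants) and Protocol Sections 5.1, 8.3.1 and 10.1.1.2 allow the same three timings. None gives an earliest or latest date.

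**Start of the window.** The documents give four starting points:
- Synopsis, Overall Design: safety assessments "will continue from the Day 180 Visit of Study VMALS-002-2 throughout the VMALS-002-2b extension study, to Day 365".
- Schedule of Activities, footnote 13: recording begins after consent, which that footnote places on Day 180.
- Protocol Section 8.3.1: "All TEAEs and TESAEs will be collected after signing informed consent prior to, on, or after Day 180 of the Study VMALS-002-2".
- SAP Section 6.14.1: collection runs from the first injection in VMALS-002-2.

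**Tabulation.** SAP Section 6.14.1 plans two tabulated sets: "TEAEs started at date of signing of IC for this study or later and all TEAEs collected during both studies". SAP Section 6.14.1.4 then sends every TEAE that began before extension consent to a listing and excludes it from the tables.

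**Population.** The Safety Population is "all Participants who enroll in VMALS-002-2b" in Protocol Section 9.2 and "all Participants who sign the Informed Consent of the VMALS-002-2b study" in SAP Section 6.1.1. Protocol Section 5 makes completion of the core-study Day 180 Visit the condition for enrolment. The glossary (Protocol Section 10.3.2) defines a Participant as someone consented "on or prior to Day 180 of VMALS-002-2". SAP Section 9 declares no changes to the protocol's planned analysis.

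**Missing start dates.** Under SAP Section 6.2.5, if the start date is wholly missing and the event is ongoing or stopped on or after first dose, "the start date will be imputed as the date of the first dose of study drug". Section 6.2.4 lets other eCRF data override this.

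**The concern.** The incidence of TEAEs, TESAEs and AESIs by treatment group is a primary endpoint. It is reported descriptively, and the adverse-event outputs listed in SAP Section 6.14.1.4 include no exposure-adjusted rate. A crude incidence can be read only if everyone is observed over the same, known period. Here the period opens on an administrative date that can fall on either side of Day 180. Two participants with identical event histories could be counted differently because one signed earlier. With no more than 18 people, a few such cases would visibly change the percentages, and the programmer has no rule for choosing between the conflicting passages.

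**Working it through.** The plan gives no figure to reproduce: this endpoint has no test, power or sample-size calculation. The check is a comparison of the passages, followed by illustrative arithmetic.

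**1. Where an event goes under each rule**

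| Rule | Onset after early consent, before Day 180 | Onset after Day 180, before late consent |
|---|---|---|
| Synopsis | Before the window | In the window |
| Schedule footnote 13 | Not addressed | Not recorded, if read literally |
| Protocol 8.3.1 | In the window | Not collected, if read literally |
| SAP 6.14.1, extension set | In | Out |
| SAP 6.14.1, cumulative set | In | In, if collected |
| SAP 6.14.1.4 | Tabulated | Listed only |

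The two columns get different answers depending on the passage used. The last two rows conflict directly in the right-hand column. There is also a smaller mismatch. SAP 6.14.1 cuts by date and 6.14.1.4 by date and time, while 6.2.5 imputes a missing time only on the first-dose date. A consent-day event with no time therefore cannot be classified under 6.14.1.4.

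**2. Length of the window**

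The nominal span is 365 − 180 = 185 days. The synopsis calls it 180 days, and Section 10.3.2 treats day numbers as visit labels, so 185 is approximate. Let d be the consent day minus 180. The consent-anchored window is 185 − d days, and the share lost (d > 0) or added (d < 0) is |d|/185. The values of d are assumptions.
- d = +30: 155 days, 30/185 = 16.2% lost.
- d = +60: 125 days, 60/185 = 32.4% lost.
- d = −30: 215 days, with 30 core-study days added.
- d = −60: 245 days, with 60 core-study days added.

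Section 10.1.1.2 requires consent before any study procedure, and the first scheduled ones are at Day 240 ± 7. Consent at that visit is thus the practical latest case for anyone attending it: 53 to 67 days after Day 180, or 53/185 = 28.6% to 67/185 = 36.2%.

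**3. Effect on incidence**

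Assume a constant hazard and a true incidence p over 185 days. The consent-anchored incidence is 1 − (1 − p)^((185 − d)/185).

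| p | d = −60 | d = −30 | d = +30 | d = +60 |
|---|---|---|---|---|
| 30% | 37.6% | 33.9% | 25.8% | 21.4% |
| 50% | 60.1% | 55.3% | 44.1% | 37.4% |

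**4. Effect on event counts**

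The synopsis reports 79 AEs among 18 participants followed for 9 months in VMALS-001. If all 18 were followed in full, that is 79/(18 × 9) = 0.488 per participant-month, or 0.0160 per day (month = 30.4375 days). An offset of 30 days moves about 0.48 events per participant and 60 days about 0.96. If all 18 were offset equally, which is an extreme case, the totals are 8.7 and 17.3. The extension has no injections, and 26 of the 79 were injection site reactions. Without them, 53/162 = 0.327 per month gives about 0.32 and 0.64 events per participant.

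**5. Population**

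Someone who signs early and never completes Day 180 is in the SAP population but is ineligible under Protocol Section 5. Someone who signs late satisfies Protocol 9.2 and SAP 6.1.1 but is not a Participant under Section 10.3.2. Each such person is at least 1/18 = 5.6% of the population.

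**6. Missing start date**

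An event first reported in the extension with no start date, and with no other eCRF data against it, is dated to first dose. That precedes extension consent, so the event leaves the extension set.

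**The case against.** A reader might infer that events between Day 180 and a late signature are lost, with neither study covering them. The documents do not establish that. The synopsis continues assessment from the Day 180 Visit, SAP Section 6.14.1 collects from first injection, and its cumulative set would include these events. The core protocol is not among the documents, so when its own collection ends is unknown. What stands is narrower. The events are outside the extension set, they go uncollected only if Section 8.3.1 or footnote 13 is applied literally, and SAP Section 6.14.1.4 contradicts the cumulative tabulation that would recover them.

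A reader might also infer that the Safety Population depends on the consent date. SAP Section 6.1.1 depends on whether consent was signed, not when; only the glossary uses a date. Protocol 9.2 and SAP 6.1.1 differ only for an early signer who does not complete Day 180, and nothing shows that this is common.

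Three further points limit the harm. Protocol Section 10.1.3 places the full explanation of the extension on Day 180, so many offsets may be small. Participants and site staff stay blinded (Section 6.1.2), so no link between consent date and arm is shown; the damage is to interpretability rather than a demonstrated bias. Clinically significant laboratory values, the other primary endpoint, are sampled at Day 240 and Day 365/ET and are much less affected. The imputation problem is confined to wholly missing dates, and such an event would still belong in the cumulative set. These points limit the size but do not remove the need for one stated start.

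**Conclusion.** The concern holds as an inconsistency with consequences for the primary tabulation. The window has four stated starts. The SAP's extension set uses the consent date, which admits core-study events after early consent and omits post-Day-180 events before late consent. Whether the omitted events appear in any table is undecided. The documents give no distribution of consent dates, so the actual size cannot be derived. Under assumed offsets of 30 or 60 days, 16% or 32% of the nominal window is affected, and an assumed 30% incidence could read anywhere from 21.4% to 37.6% across offsets of +60 to −60 days, on a constant hazard and with everyone offset alike. No formal test is planned, so only descriptive incidence is affected. The population and glossary wording and the missing-date rule are separate, smaller inconsistencies that belong in the same correction.

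**What to change.** - **Extension set:** for everyone, onset after completion of the Day 180 Visit through Day 365/ET. **Cumulative set:** onset from first injection in VMALS-002-2. Put both in footnote 13 of the Schedule of Activities, Protocol Section 8.3.1 and SAP Sections 6.14.1 and 6.14.1.4, with one rule for an event on the visit day that has no time.
- **SAP Section 6.14.1.4:** delete or limit the bar on tabulating pre-consent TEAEs so that the cumulative tables stand.
- **Late consenters:** at consent, collect events since Day 180 retrospectively. Protocol Section 6.3 already uses Day 180 as the start for concomitant medications. State the earliest and latest acceptable consent dates.
- **Safety Population:** in Protocol Section 9.2 and SAP Section 6.1.1, everyone who completed the Day 180 Visit and signed extension consent at any time. Remove "on or prior to Day 180 of VMALS-002-2" from Protocol Section 10.3.2.
- **Missing start date:** for an event first reported in the extension, with the start date wholly missing and no contradicting data, impute the day after the Day 180 Visit for the extension set.

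The cost is wording in both documents and one anchor date in the programming. There are two small downsides: events before a late consent rest on recall or records, and the imputation may place a few core-onset events in the extension set.
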